6.5. Previous and Concomitant Medications and Therapies

At Screening (Visit 1), the investigator or designee will question the subject to ensure they have not used any excluded therapies (Section 6.5.2).

6.5.1. Permitted Concomitant Therapies and Over the Counter Products (OTC)

Concomitant therapies are any new or existing therapies received from Screening (Visit 1) until Day 393 (Visit 16). Concomitant therapies include drug (e.g. prescription and over the counter [OTC]), and non-drug (e.g., chiropractic, physical therapy, energy-based treatments).

Subjects will be allowed to use therapies not restricted by the protocol if they have been on a stable dose prior to study entry. Vitamins, minerals, and dietary supplements are permitted while on

study if the subject has been on a stable dose prior to study entry and, in the opinion of the Investigator, will not affect the safety or efficacy of the subject during the study. Topical hair/scalp products (shampoos, conditioners, other products) should be reviewed by the Investigator and are permitted if, in the Investigator's opinion, they will not affect the safety, pharmacokinetic or pharmacodynamic assessments of the subject during the study.

Topical therapies such as topical corticosteroids are permitted if they are not applied on or near the scalp. Inhaled or intranasal corticosteroids are allowed in the study.

Prior permitted concomitant medications taken within 30 days of beginning treatment with study medication will be documented in the subject's source document and eCRF. In addition, any new permitted medications administered during protocol treatment and through Week 56 (Visit 16) will be documented in the subject's source document and eCRF.

6.5.2. Prohibited and/ or Restricted Medications

Any medication, shampoo or hair/ scalp product known to affect hair growth in AU or AT is prohibited throughout the study period. Subjects who are on a stable dose of finasteride for benign prostatic hypertrophy for greater than 1 year, are eligible for enrollment into the study as long as they maintain the same stable dose throughout the study. Since subjects with known AGA are excluded from the study, treatment with finasteride for alopecia during the study and within one year prior to study enrollment is prohibited.

A list of medications and therapies that require a specific washout period prior to study entry and are not permitted during the study is in Table 1.

Table 1: Prohibited Medications

Therapy/Medication	Washout Period
Systemic Therapies	
Disease Modifying Anti-Rheumatic Drugs (DMARDs), Biologics or immunosuppressants, such as: anakinra, adalimumab, azathioprine, corticosteroids, cyclosporine, etanercept, infliximab, methotrexate, TNF inhibitors, ustekinumab	1 month or 5 half-lives whichever is greater
Plaquenil	2 months
JAK inhibitors (oral or topical)	Prior or current treatment with a JAK inhibitor is prohibited at any time
Intralesional Steroids on the Scalp	
Topical Treatments on the Scalp	
Anthralin, bimatoprost, corticosteroids, diphenycprone, diphenylcycloprophenone (DPCP), Squaric acid dibutylester (SADBE), minoxidil, pimecrolimus, tacrolimus	1 month
Phototherapy, Laser Therapy, Excimer Laser	
	3 months

6.6. Subject Identifier (SI)

The investigator will assign a unique five-digit subject identifier (SI) to each subject at Screening (Visit 1).

The SI format will be NN-NNN, using leading zeroes as appropriate, where:

- The first 2 digits are the investigational center site number assigned by Aclaris
- The final 3 digits are the subject number (SN), assigned in ascending numerical order by the investigator or designee, without omitting or repeating any number, starting with 001.

For example, the SI for the twenty-third subject that signs an informed consent form at site number 01 would be 01-023. The subject will be identified using the SI in all study documentation for the duration of the study.

6.7. Replacement Subjects

Subject enrollment will continue until approximately 12 subjects have been randomized. Subjects who are randomized and do not complete the study will not be replaced.

6.8. Subject Withdrawal Criteria

Subjects will be informed that they are free to withdraw from the study at any time and for any reason. The Investigator may remove a subject from the study if, in the Investigator's opinion, it is not in the best interest of the subject to continue the study. Examples of other reasons subjects may be discontinued from the study are: a change in compliance with an inclusion or exclusion criterion, occurrence of AEs, occurrence of pregnancy or use of a prohibited therapy. The Investigator or designee must inform the Aclaris Therapeutics, Inc. study monitor of any subject discontinuation. (Refer to Section 10.2.4 for study medication discontinuation or termination criteria).

In case of premature discontinuation of study participation, all efforts will be made to perform all Week 56 (Visit 16) assessments. The date the subject is withdrawn from the study and the reason for discontinuation must be recorded in the subject's electronic case report forms (eCRFs). All withdrawn subjects with ongoing AEs will be followed until the event has resolved or stabilized, until the subject is referred to the care of a local health care professional, or until a determination of a cause unrelated to the study medication or study procedures is made.

6.9. Study Termination

This study may be terminated prematurely in whole or in part due to a change in the benefit/risk profile for ATI-50002 Topical Solution such that continuation of the study would not be justified on medical, business, or ethical grounds. This determination may be made by the Study Investigators in conjunction with the Sponsor, or by IRB or the U.S. Food and Drug Administration (FDA). The Sponsor may also elect to terminate the study if enrollment is sufficiently slow to prevent the completion of the study in an acceptable timeframe, or if ATI-50002 development is discontinued.

If the study is terminated prematurely, the Sponsor will notify the Study Investigators and the FDA. The Investigator must promptly notify all enrolled subjects and the IRB of study termination.

7. INVESTIGATIONAL PLAN

7.1. Overall Study Design

In the double-blind period, this Phase 2, multicenter, randomized study is designed to evaluate the safety, tolerability, pharmacokinetics and pharmacodynamics of ATI-50002 Topical Solution in subjects with AU and AT. Subjects will be required to have a clinical diagnosis of stable, clinically typical AU or AT for a duration of at least six months up to and including seven years. A total of 12 subjects will be randomized.

During the screening period, subjects will be assessed for eligibility into the study. Subjects who meet all the entry criteria will be randomized 2:1 to ATI-50002 Topical Solution, 0.46% or Vehicle Topical Solution and will apply a minimum of 1.5 mLs up to a maximum of 4 mLs of study medication to the entire scalp twice-a-day for 28 days. On Day 1 (Visit 2), Day 28 (Visit 6), and Day 196 (1 day prior to Visit 13), subjects will apply study medication once-a-day.

Blood samples for concentrations of ATI-50002 will be collected from the first 6 subjects enrolled into the study on Day 1 (Visit 2), and Day 28 (Visit 6) at pre-dose and 1, 2, 4, 8 hours post dose and on Day 2 (Visit 3) and Day 29 (Visit 7), 24 hours post-dose. Blood samples for immunology will be collected on Day 1 (Visit 2) before study medication application, and on Day 29 (Visit 7), 24 hours after study medication application on Day 28 (Visit 6). A 4-mm punch biopsy of the scalp will be obtained to determine the concentration of ATI-50002 in the scalp skin on Day 2 (Visit 3) 24 hours after study medication application on Day 1 (Visit 2) and on Day 29 (Visit 7), 24 hours after study medication application on Day 28 (Visit 6). A 4-mm punch biopsy will be obtained to determine histology and immunology prior to study medication application on Day 1 (Visit 2). Additional 4-mm punch biopsies to determine histology and immunology will be collected on Day 29 (Visit 7) and Day 197 (Visit 13), 24 hours after study medication application on Day 28 (Visit 6) and Day 196. Safety and tolerability will be evaluated at each study visit by assessment of adverse events and vital signs, and at select visits, ECGs and clinical laboratory tests will be completed.

On Day 29 (Visit 7) subjects who complete Visit 7, continue to meet the entry criteria and have no clinically significant AEs or tolerability issues will be eligible to enter a 12-month open-label extension. In the open-label extension, safety, tolerability and efficacy will be assessed. All subjects enrolled in the open-label extension will apply ATI-50002 Topical Solution, 0.46% to the entire scalp, twice daily for 52 weeks (12 months). In addition, subjects with eyebrow loss may apply a thin film of study medication to the affected eyebrow(s) twice-daily for 52 weeks (12 months). Subjects will be followed for safety, tolerability and efficacy as detailed in Section 7.3. Subjects who decline or are not eligible for the open-label extension should be seen for suture removal, if applicable per Section 7.3 and Visit 16 (Post-treatment) 30 days \pm 3 days following the Day 28 (Visit 6). Subjects enrolled in the initial 6-month Open Label Extension outlined by Protocol Amendment 1 (dated 06Feb2018) must be re-consented under Protocol

Amendment 2 (dated 14AUG2018) in order to continue for an additional 6 months of Open Label treatment.

7.2. STUDY PROCEDURES

The investigator or a designated and appropriately trained staff member should perform the study assessments according to the schedule of assessments. The same staff member should perform the assessments for a given subject throughout the study. If this becomes impossible, an appropriate designee with overlapping experience with the subject and study should perform the assessments. The same lighting conditions and subject positioning should be used for all evaluations for a given subject.

7.3. Schedule of Assessments

	Screening	Baseline	Double Blind Treatment							Optional Visit (Suture Removal)
	Visit 1	Visit 2	Visit 3	Visit 4	Visit 5	Call	Visit 6	Visit 7		
Week		0	0	1	2	4	4	4		6
Treatment Day	-30 to 0	1	2	8	15	27	28	29		43
Treatment Window(days)	N/A	N/A		± 3	± 3	-3	-3	-3		± 3
Informed consent ¹	X								X ¹⁷	
Inclusion/exclusion criteria	X	X								
Physical exam ²	X								X	
Demographics & medical history	X									
Alopecia Areata History	X									
Vital signs ³	X	X	X	X	X		X	X		X
Clinical laboratory sampling ⁴ : CBC, Chemistry with lipids, Virology, Serum Pregnancy, Urinalysis	X ⁴	X			X			X		
Urine pregnancy test (WOCBP) ⁵		X						X		
ECG	X	X			X			X		
SALT Score (prior to ALODEX) ⁶		X							X	
ALODEX Score (after SALT) ⁷		X							X	
Clinician Eyebrow Assessment									X ¹⁸	
Subject Eyebrow Assessment									X ¹⁸	
Subject Global Impression of Treatment Satisfaction (SGIS)										
Photography ⁸		X							X	
Subject randomization		X								
Subject instructions ⁹			X	X	X	X	X	X	X ¹⁷	
Biopsy for PK ¹⁰				X						X
Biopsy for PD ¹¹			X							X
Blood sample for PK ¹²			X	X				X	X	
Blood for immunologic studies ¹³			X							X
Dispense, collect, weigh study medication bottles ¹⁴			X	X	X	X		X	X ¹⁷	
In office study medication application ^{9,14}			X					X		
Suture removal, if applicable ¹⁵						X				X
Telephone Call ¹⁶							X			
Concomitant therapies			X		X	X	X	X	X	X
Adverse events			X	X	X	X	X	X	X	X

	Open-Label Treatment										Post-Treatment ¹⁷
	Visit 8	Visit 9	Visit 10	Visit 11	Visit 12	Call	Visit 13	Optional Visit (Suture Removal)	Visit 14	Visit 15	Visit 16
Week	8	12	16	20	24	28	28	30	40	52	56
Treatment Day ¹⁷	57 (OLE 28)	85 (OLE 56)	113 (OLE 84)	141 (OLE 112)	169 (OLE 140)	196 (OLE 167)	197 (OLE 168)	211 (OLE 182)	281 (OLE 252)	365 (OLE 336)	59/ 393 (OLE 364)
Treatment Window(days)	± 3	± 3	± 3	± 3	± 3	± 3	± 3	± 3	± 7	+7	± 3/± 7
Informed consent ¹											
Inclusion/exclusion criteria											
Physical exam ²											X
Demographics & medical history											
Alopecia Areata History											
Vital signs ³	X	X	X	X	X		X	X	X	X	X
Clinical laboratory sampling ⁴ :		X					X		X	X	X
CBC, Chemistry with lipids, Virology, Serum Pregnancy, Urinalysis											
Urine pregnancy test (WOCBP) ⁵	X	X	X	X	X		X		X	X	X
ECG		X					X				X
SALT Score (prior to ALODEX) ⁶	X	X	X	X	X		X		X	X	X
ALODEX Score (after SALT) ⁷	X	X	X	X	X		X		X	X	X
Clinician Eyebrow Assessment	X	X	X	X	X		X		X	X	X
Subject Eyebrow Assessment	X	X	X	X	X		X		X	X	X
Subject Global Impression of Treatment Satisfaction (SGIS)	X	X	X	X	X		X		X	X	
Photography ⁸	X	X	X	X	X		X		X	X	
Subject randomization											
Subject instructions ⁹	X	X	X	X	X		X		X	X	
Biopsy for PD ¹¹							X				
Blood for immunologic studies ¹³							X				

	Open-Label Treatment										Post-Treatment ¹⁷
	Visit 8	Visit 9	Visit 10	Visit 11	Visit 12	Call	Visit 13	Optional Visit (Suture Removal)	Visit 14	Visit 15	Visit 16
Week	8	12	16	20	24	28	28	30	40	52	56
Treatment Day¹⁷	57 (OLE 28)	85 (OLE 56)	113 (OLE 84)	141 (OLE 112)	169 (OLE 140)	196 (OLE 167)	197 (OLE 168)	211 (OLE 182)	281 (OLE 252)	365 (OLE 336)	59/393 (OLE 364)
Treatment Window(days)	± 3	± 3	± 3	± 3	± 3	± 3	± 3	± 3	± 7	+7	± 3/± 7
Dispense, collect, weigh study medication bottles ¹⁴		X	X	X	X	X	X		X	X	
In office study medication application ^{9,14}		X									
Suture removal, if applicable ¹⁵								X		X	
Telephone Call ¹⁶						X					
Concomitant therapies		X	X	X	X	X	X	X	X	X	X
Adverse events		X	X	X	X	X	X	X	X	X	X
¹ A written signed ICF must be obtained from each subject prior to performing any study related procedure (i.e., prior to performing vital signs, standardized photography, biopsies, clinical laboratory sampling, or UPT).											
² A physical exam includes: General appearance, examination of head, eyes, ears, nose and throat, respiratory, cardiovascular, abdominal, neurological, musculoskeletal, lymphatic and skin assessment.											
³ Vital signs include oral or ear temperature, blood pressure, heart rate, respiration rate (height and weight at Baseline only).											
⁴ Clinical laboratory sampling includes: CBC, Chemistry with lipids, Urinalysis, at each visit and At Screening only: Quantiferon Gold, TIBC, Serum iron, Serum Ferritin, Serum pregnancy, T3, T4, and TSH.											
⁵ UPT must be performed prior to randomization at Visit 2 and prior to study medication application at Day 28 (Visit 6) and at each OLE visit. UPT must be negative for the subject to continue in the study. WOCBP must have a negative serum pregnancy test at screening and a negative UPT at baseline prior to randomization.											
⁶ SALT is performed prior to ALODEX score using device provided.											
⁷ ALODEX is performed after SALT score using device provided.											
⁸ Photography should be performed on Day 1 (prior to application of study medication application) and on Day 29 & Day 197 prior to the scalp biopsy.											
⁹ Subjects must be instructed to apply the study medication according to the instructions in Appendix 1. Subjects will apply the first dose of study medication on the morning of Day 1 (Visit 2) and the last application of study medication on the morning of Day 28 (Visit 6), under the instruction and supervision of the study staff. Study medication at these visits should be applied in the morning to allow the 8-hour post dose assessments to occur at a reasonable time. On Day 1 (Visit 2) and Day 29 (Visit 7) subjects will only apply study medication once-a-day in the office.											
¹⁰ PK: A 4mm punch biopsy must be obtained on Day 2 (Visit 3) and Day 29 (Visit 7) 24 hours (± 30 minutes) after study medication application on Day 1 (Visit 2) and Day 28 (Visit 6).											
¹¹ PD: A 4mm punch biopsy must be obtained on Day 1 (Visit 2) before application of first dose of study medication and Day 29 (Visit 7) 24 hours (± 30 minutes) after study medication application. Subjects that choose to continue in to open-label extension treatment will also have a 4mm punch biopsy collected on Day 197 (Visit 13).											
¹² PK: The first 6 subjects enrolled in the study will have the blood PK testing performed. Blood for PK sampling will be obtained on Day 1 (Visit 2) and Day 28 (Visit 6), just prior to study medication application (predose), and 1, 2, 4, 8 hours post dose and on Day 2 (Visit 3) and Day 29 (Visit 7), 24 hours after study medication application (on Day 1 (Visit 2) and Day 28 (Visit 6). See Section 9.3.2 for PK sample draw time windows.											

	Open-Label Treatment										Post-Treatment ¹⁷
	Visit 8	Visit 9	Visit 10	Visit 11	Visit 12	Call	Visit 13	Optional Visit (Suture Removal)	Visit 14	Visit 15	
Week	8	12	16	20	24	28	28	30	40	52	56
Treatment Day ¹⁷	57 (OLE 28)	85 (OLE 56)	113 (OLE 84)	141 (OLE 112)	169 (OLE 140)	196 (OLE 167)	197 (OLE 168)	211 (OLE 182)	281 (OLE 252)	365 (OLE 336)	59/393 (OLE 364)
Treatment Window(days)	± 3	± 3	± 3	± 3	± 3	± 3	± 3	± 3	± 7	+7	± 3/± 7
¹³ Blood for immunology will be obtained prior to administration of study medication on Day 1 (Visit 2) and on Day 29 (Visit 7) 24 hours (± 30 min) after study medication application on Day 28 (Visit 6). Subjects that choose to continue in to open-label extension treatment will also have blood for immunology collected on Day 197 (Visit 13).											
¹⁴ On Day 1 (Visit 2) and Day 28 (Visit 6) the study medication bottle should be weighed and then dispensed to the subject for the initial application under the supervision of study staff in the office. After the initial application on Day 1, the study medication bottle should be collected, weighed and dispensed to the subject after the 24-hour post-dose blood draw on Day 2 (Visit 3). For Visits 3 -6, each study medication bottle (with the cap) must be weighed before dispensing to the subject and at the time of return using the scale provided by Aclaris. On Day 28 (Visit 6), the study medication bottle should be weighed after subject applies the study medication in the office and not redispensed.											
¹⁵ The investigator or designee will remove the sutures approximately 14 days after scalp biopsy, unless an absorbable suture is used.											
¹⁶ On Day 27 or the day prior to Day 28 (Visit 6), the study staff will call the subject to remind them not to apply study medication on the morning of Day 28 (Visit 6) and to bring both used and unused study medication bottles to the visit. Study medication will be applied in the office under the supervision of the study staff. On Day 196 or the day prior to Week 28 (Visit 13) the study staff will call the subject to remind them not to apply study medication in that evening and on the morning of Week 28 (Visit 13), and to bring both used and unused study medication bottles to the visit. The scalp biopsy at Week 38 (Visit 13) should be performed 24 hours (±30 minutes) post the last study medication application.											
¹⁷ On Day 29 (Visit 7) subject may be given the option to move into open-label extension treatment. 
 • If the subject declines the open-label extension, she/he should be seen for the Visit 16 (Post-treatment) assessments 30 days following the date of Day 29 (Visit 7). • If the subject chooses to continue in to the open-label extension, she/he must sign an ICF prior to being dispensed open-label drug and receiving continued study medication application instructions. • If the subject enrolls in open-label treatment after Day 29 (Visit 7), an unscheduled visit will be conducted in order to obtain consent, review drug application instructions, and dispense drug. This will be considered the official date that the subject initiated open-label extension treatment and the scheduling of subsequent visits 8-16 should be based off of this date as referenced by (OLE xxx) in the treatment day schedule header above. 											
¹⁸ Subjects who are eligible and consent to enter the open-label extension will have a baseline CEA and SEA completed at Visit 7 or the unscheduled Visit.											

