8.3. Application of Study Medication

At Visit 2 (Day 1), the investigational center staff member will instruct each subject to apply a minimum of 1.5 mL up to a maximum of 4-mL dose of ATI-50002 Topical Solution, 0.46% or Vehicle Topical Solution, twice-daily to the entire scalp; once in the morning and approximately 12 hours later following the instructions in APPENDIX 1. On Day 1 (Visit 2) and Day 28 (Visit 6), study medication will be applied once-a-day due to the 24-hour PK and PD assessments. The subject must wash his/her hands thoroughly before and after each study medication application. The predose PK sample should be drawn and the baseline PD scalp biopsy should be obtained prior to study medication application. The subject should apply a thin film of the assigned study medication to his/her entire scalp and gently rub in the study medication.

On Day 1/ Baseline (Visit 2) the investigational staff member will:

- Dispense the appropriate study medication bottle.
- Weigh the bottle with the cap prior to the first study medication application and record in the subject's source document.
- Instruct the subject on the appropriate application technique (APPENDIX 1).

- Instruct the subject not to apply study medication to the biopsy site and to avoid contact with the eyes.
- Observe the subject's first study medication application to ensure proper coverage and monitor the subject for at least 20 minutes. Collect the study medication bottle.
- Record the first application completion time.
- Weigh the bottle with the cap after study medication application and record the weight in the subject's source document.
- Redisperse study medication after the 24-hour PK and PD blood and biopsy sample collections on Day 2 (Visit 3).

On Day 28 (Visit 6) the investigational staff member will:

- Collect and weigh all study medication bottles (with the cap on the bottle) returned from the subject and record weight(s) in the subject's source document.
- Select one study medication bottle for the Day 28 (Visit 6) application.
- Weigh the bottle and cap prior to study medication application and record weight in the subject's source document.
- Review the application instructions with the subject (APPENDIX 1).
- Instruct the subject to avoid contact with the eyes.
- Observe the subject's study medication application to ensure proper coverage. Collect the study medication bottle after application.

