9.3.2. Blood Samples (Double-blind Period)

For the first six subjects enrolled into the study, blood samples for PK analysis of ATI-50002 will be collected by a qualified staff member. On Baseline/ Day 1 (Visit 2) and Day 28 (Visit 6) blood samples will be collected at predose (0-hour) (just prior to study medication application in the morning) and then at the following times **after study medication application**:

- 1 hour (\pm 5 minutes)
- 2 hours (\pm 10 minutes)
- 4 hours (\pm 10 minutes)
- 8 hours (\pm 10 minutes)

On Day 2 (Visit 3) and Day 29 (Visit 7)

- 24 hours (\pm 30 minutes)

The bioanalytical laboratory will provide instructions on the collection and shipment of samples.

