12.4. Pharmacokinetic Analyses

Blood Samples

Blood samples for analysis of the concentration of ATI-50002 will be taken from the first 6 subjects enrolled into the study on Baseline/Day 1 (Visit 2) and Day 29 (Visit 7) at predose (0 hr), and 1, 2, 4, 8 hours after study medication application and on Day 2 (Visit 3) and Day 29 (Visit 7), 24 hours post dose. For each subject, standard PK parameters (C_{max} , T_{max} , AUC_{0-t} , $AUC_{0-\infty}$, $t_{1/2}$) will be calculated, as a minimum and whenever possible, based on the plasma concentrations of ATI-50002.

Scalp Biopsy

The concentration of ATI-50002 in skin will be determined in a 4-mm punch biopsy of the scalp taken on Day 2 (Visit 3) and Day 29 (Visit 7) 24 hours post study medication application in the office on Day 1(Visit 2) and Day 28 (Visit 6).

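### Footnote 9 of the schedule and Protocol Section 12.4 contradict themselves and other sections on whether the end-of-double-blind application and serial blood samples fall on Day 28 or Day 29

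*Protocol*

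**What the plan says.** Footnote 9 gives two days. One sentence has subjects make "the last application of study medication on the morning of Day 28 (Visit 6"), supervised by study staff. Its final sentence reads "On Day 1 (Visit 2) and Day 29 (Visit 7) subjects will only apply study medication once-a-day in the office". The SAP copy of the schedule (SAP Section 3) carries the same footnote.

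Section 12.4 places the second serial blood profile "on Baseline/Day 1 (Visit 2) and Day 29 (Visit 7) at predose (0 hr), and 1, 2, 4, 8 hours after study medication application". The same sentence then places the last sample "on Day 2 (Visit 3) and Day 29 (Visit 7), 24 hours post dose". The scalp-biopsy paragraph of Section 12.4, however, refers to an office application on Day 28.

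Other sections read differently:

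- **Application day.** Section 8.3 states "On Day 1 (Visit 2) and Day 28 (Visit 6), study medication will be applied once-a-day due to the 24-hour PK and PD assessments". The Synopsis and Sections 4.1, 7.1 and 8.1, and SAP Section 2, also name Day 28 as a once-daily day.
- **Serial blood samples.** Section 9.3.2 states "On Baseline/ Day 1 (Visit 2) and Day 28 (Visit 6) blood samples will be collected at predose (0-hour"), with the 24 h sample on Day 29. The Synopsis, Section 7.1, footnote 12 and SAP Section 2 agree.
- **Visit 7 samples.** Footnotes 10 and 13 and Section 9.3.1 tie the PK biopsy and the immunology blood to 24 h ± 30 minutes after the Day 28 application.
- **Bottle handling.** Footnote 14 and Section 8.3 have the site keep the bottle after the Day 28 application.

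**The concern.** The end-of-double-blind PK and PD samples serve the primary objective, and their meaning depends on the time since the last application. The Visit 7 scalp level is summarised beside the Day 2 level, and both are meant to be 24-hour values. If sites follow different sentences, the two time points are no longer alike, and neither are subjects within Visit 7.

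The text leaves some room for this. Section 8.3 says that on Day 2 medication is redispensed only after the 24-hour collections, but no matching order is given for Visit 7. Footnote 17 allows open-label drug to be dispensed at Visit 7, so drug may be on hand on the day that footnote 9 names for an office application. Open-label drug is active for everyone. If it were applied before sampling, a former vehicle subject's Visit 7 biopsy would come from actively treated skin. Footnote 11 and Sections 9.2.1 and 9.2.2 time the Day 29 PD samples from the application without naming its day, although the Synopsis, Section 7.1 and (for blood) footnote 13 do name it.

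**Working it through.** This is calendar arithmetic. Inputs: visit days and the ± 30 minute window (Section 7.3 and its footnotes, Section 9.3.2); doses about 12 h apart (Section 8.3); at most 28 days of double-blind application (Synopsis, Section 7.5). A morning application and morning sampling at 08:00 are my assumption.

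1. **The plan's own figure.** Day 28 08:00 to Day 29 08:00 = 24 h. The stated 24 h ± 30 minutes is reproduced if the last application is on the morning of Day 28.

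2. **Section 12.4 as written.** An application on Day 29 at 08:00 leaves 24 − 8 = 16 h of Day 29. The 24 h point is Day 29 + 1 = Day 30. The next scheduled contact after Visit 7 is the optional suture visit on Day 43. Predose, 1, 2, 4, 8 and 24 h samples cannot all follow one application and fall on Day 29.

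3. **Final sentence of footnote 9.** The result depends on what a site does:

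| Reading | Latest application before the Visit 7 sample | Interval |
|---|---|---|
| (a) Day 29 application made before sampling | Day 29 morning | about 0 h |
| (b) Day 28 treated as an ordinary twice-daily day, sampling before any Day 29 application | Day 28, about 20:00 | about 12 h |
| (c) Day 28 morning only, Day 29 application made after sampling | Day 28 morning | 24 h |

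Readings (a) and (b) are far outside ± 30 minutes. Reading (c) is on time.

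4. **Dose count.** Once-daily on Days 1 and 28: 1 + 26 × 2 + 1 = 54 applications over 28 days. Once-daily on Days 1 and 29, with twice-daily use between: 1 + 27 × 2 + 1 = 56 applications over 29 days, one day beyond the stated 28-day maximum.

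5. **What reaches the analysis.** SAP Section 4.5 summarises scalp levels at Visits 3 and 7. SAP Section 4.2.1 only lists blood levels, which come from the first 6 subjects. SAP Section 4.8 drops scalp histology and sends ALADIN and blood T-cell analyses to a separate document.

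**The case against.** The strongest reply is that the protocol must be read as a whole. Footnotes 10, 12 and 13 and Sections 9.3.1 and 9.3.2 fix the Visit 7 sampling times without relying on the last sentence of footnote 9. Section 8.3 sets out the Day 28 application step by step and then withholds the bottle. The reminder call, the confinement period and Appendix 1 also point to Day 28. A site would have to disregard all of this to dose before sampling. On this view both passages are drafting slips, and the error in Section 12.4 sits in an analysis section, not in the sampling instructions.

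Most of that stands, and it limits the risk. It does not remove the contradiction: footnote 9 is operative text in both documents, and Section 12.4 cannot be carried out as written.

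A reader might infer more than the documents support:

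- **That Visit 7 samples will be mistimed.** This follows only under readings (a) and (b).
- **That these are the only end-of-treatment PK and PD samples.** The serial plasma samples that other sections place on Day 28 also belong to the end of treatment, and extension subjects have PD samples again at Visit 13.
- **That a truncated AUC would harm the reported results.** Protocol Section 12.4 plans PK parameters, but the SAP only lists blood levels.
- **That the error can be sized from the oral half-life.** With about 9.0 h (Protocol Section 3.1) and first-order decline, plasma at 12 h would be 2^(12/9) = 2.5 times the 24 h level (2.0 to 4.0 for assumed half-lives of 12 to 6 h). That half-life comes from an oral prodrug in healthy volunteers and concerns plasma. No scalp half-life is given, so the effect on the summarised endpoint cannot be quantified.

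**Conclusion.** The point holds as an internal inconsistency in the application and sampling schedule for a primary PK/PD objective. Footnote 9, in both copies, contradicts itself. The impossibility in Section 12.4 is unconditional as written. The mistiming from footnote 9 is conditional: it needs an application at Visit 7 before sampling, or an evening application on Day 28. The interval would then be about 0 h or about 12 h instead of 24 h ± 30 minutes, given morning visits and doses about 12 h apart.

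The exposure is the Visit 7 scalp concentration in up to 12 subjects, and the ALADIN and blood immunology samples at the end of the double-blind period. Blood PK is limited to 6 subjects and is only listed. Nothing in the documents shows that any sample was in fact mistimed. That most passages give Day 28 does not settle the clinical question here; the sponsor must decide it. The correction should be made because it is cheap and the timing defines the measurement.

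**What to change.** 1. Reconcile footnote 9 (protocol and SAP copies) and Section 12.4 with the other passages, so that the supervised application, the serial blood samples and the 24 h samples agree throughout.
2. Have the sponsor state explicitly the order of application and sampling at Visit 7, including for subjects who receive open-label drug that day.
3. In the PK and PD listings, compute the time from the latest recorded application to each Visit 7 sample, and flag any outside 24 h ± 30 minutes. Section 8.3 already has the site record when the Day 28 application was completed. Where the time of a later application was not captured, show the interval as unknown.

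The cost is a sentence in each copy of footnote 9, one in Section 12.4, one on the order at Visit 7, and one derived column in the listings. SAP Section 4.6 reports the interim PK assessment of the first 6 subjects as already done, so new wording cannot change those samples. The flag still shows which of them were on time.
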